1.3.2. Preliminary Unpublished Data (blinded)

Subject Disposition and Baseline Characteristics (data-cutoff May 19, 2015)

Thirty-six subjects have been randomized, of which 12 have completed the study. To date, three subjects have discontinued from the study. One subject in Cohort 4 was no longer willing to participate and discontinued on Day 8; this subject was replaced with another subject. Two other subjects were no longer willing to participate in the study and were terminated early (1 each in the 1.0 mg/kg cohort and the 3.0 mg/kg cohort) and were not replaced.

The baseline characteristics of the subjects randomized to date in the SAD study are summarized in Table 1 below.

Table 1. Baseline Characteristics – SAD Cohorts, Study B3501001

Characteristics	Placebo N=9	Cohort 1 (0.3 mg/kg) N=6	Cohort 2 (1.0 mg/kg) N=6	Cohort 3 (3.0 mg/kg) N=6	Cohort 4 (6.0 mg/kg) N=9
Age ^{1,2}	57.1 ± 6.5	60.7 ± 4.5	60.7 ± 6.2	57.7 ± 4.5	57.4 ± 8.7
Gender ² (M:F)	4:5	5:1	2:4	3:3	5:4
Weight ^{1,2} (kg)	89 ± 21	93 ± 9	77 ± 14	90 ± 11	88 ± 16
BMI ^{1,2} (kg/m ²)	31.0 ± 4.6	32.3 ± 3.7	29.1 ± 3.3	30.8 ± 3.2	32.1 ± 3.4
Duration T2DM ³ (years)	10.9	13.4	10.0	8.5	8.1
Baseline HbA1c ^{1,4} (%)	8.7 ± 1.0	8.1 ± 0.9	7.7 ± 0.6	8.2 ± 0.5	8.3 ± 0.7

¹ Mean ± SD; Source; ² Table 14.1.2.1 (B3501001 IND Tables); ³ Table 14.1.2.2 (B3501001 IND Tables);

⁴ Table 14.4.7.5.1 (B3501001 IND Tables).

Pharmacokinetics (data-cutoff May 19, 2015)

As of May 19th 2015, preliminary, unpublished PK of PF-06293620 are available from the first 4 cohorts (0.3, 1, 3, and 6 mg/kg) in the ongoing single ascending dose study in subjects with T2DM. Following administration of single subcutaneous doses of PF-06293620, absorption was slow with median C_{max} occurring approximately 4-10 days post dose. After that the decline in concentration was slow and multiphasic with mean terminal half-life (t_{1/2}) ranging from 9 to 18 days as the doses increased from 0.3 to 3 mg/kg. Both C_{max} and total

exposure (AUC_{inf}) increased slightly greater than dose proportionally with increasing doses up to 6 mg/kg. Table 2 below summarizes the PF-06293620 preliminary, unpublished PK parameters.

Table 2. Geometric Mean (%CV) Plasma PF-06293620 Pharmacokinetic Parameter Values, Study B3501001 (Preliminary, unpublished, based on QCed data)

Parameter	PF-06293620 Treatment			
	0.3 mg/kg SC	1 mg/kg SC	3 mg/kg SC	6 mg/kg SC
N, n	6,2	6,5	6,6	6,0
AUC _{inf} (µg·hr/mL)	260	1748 (46)	6606 (45)	NC

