3. STUDY DESIGN

3.1. Study Overview

This is a randomized, placebo-controlled, double-blind (sponsor unblinded; subjects and Investigator blinded), single dose, and multiple-dose dose escalation study of PF-06293620. The study was originally to be conducted in approximately 6 planned single-dose cohorts. Based on the preliminary, unpublished, results from the first 4 SAD cohorts, the 1 mg/kg IV cohort will be evaluated but the 10 mg/kg IV cohort will not be conducted. Approximately 4 multiple dose cohorts are planned in an effort to seek a maximum tolerated dose (MTD) and evaluate different dosages for safety and tolerability. The multiple-dose cohorts will be initiated based on a review of the preliminary, unpublished safety and PK results from the first three SAD dose cohorts. The planned dosages, the route of administration, frequency of administration and the approximate number of subjects for the SAD cohorts are shown in [Table 5](#) and for the MAD cohorts in [Table 6](#) below.

Single-Dose Cohorts:

The SAD portion will be conducted in approximately 5 planned cohorts (a 6:2 ratio of active drug to placebo) with a total of up to approximately 40 subjects in an effort to seek a maximum tolerated dose (MTD). PF-06293620 will be administered subcutaneously(SC) at doses of 0.3, 1, 3, and 6 mg/kg. In addition, a 1 mg/kg dose, will be given intravenously (IV). The screening period will last up to 28 days and the treatment period will last approximately 84 days. Subjects will be required to be on stable, daily dosages of metformin. Subjects will receive a single dose of study treatment (PF-06293620 or placebo) on Day 1, with multiple PK and safety assessments during the confinement period in Clinical Research Unit (CRU) on study Days -1, 1, 2, 3 and 4 and will be discharged on Day 5. The subjects will return to the CRU for subsequent visits at which time safety assessments, including AE monitoring, clinical laboratory tests, vital signs, and ECG, as well as PK, MMTT, lipid and PD biomarker labs will be performed (See [Schedule of Activities](#)- SAD). In each SAD cohort, the first 2 subjects will be dosed with either PF-06293620 or placebo and observed for 24 hours. If no acute toxicity is observed in the first 24 hours, as defined in [Section 3.3.1](#), the remaining subjects in the cohort will proceed with dosing of either PF-06293620 or placebo. Dose escalation will not occur until all subjects in the cohort are enrolled and at least 6 subjects in

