9.3.2. Statistical Methods of PK Analysis

The serum PK parameters for RN909 (PF-06293620) will be summarized descriptively by dose and route of administration. Serum concentrations will be listed and summarized descriptively by dose, nominal PK sampling time and route of administration. Individual subject, summary profiles (mean and median plots) of the serum concentration-time data will be plotted by treatment and PK sampling time. For summary statistics and summary plots, the nominal PK sampling time will be used. For individual subject plots, the actual PK sampling time will be used, whilst the pre-dose time will be set to zero. Summary plots will be presented on both linear-linear and log-linear scales.

Dose normalized parameters for RN909 (PF-06293620) will be plotted against dose and route of administration and will include individual subject values and the geometric means for each dose. For SAD, AUC_{inf}, AUC_{last}, and C_{max} will be plotted; for MAD, AUC_τ and C_{max} (Day 1 and Day 57) and C_{min} (Day 57) will be plotted. These plots will be used to help understand the relationship between the PK parameters and dose.

Absolute bioavailability (F) will be estimated as the ratio of dose-normalized adjusted geometric means for SC and IV for AUC_{last} and AUC_{inf} . Dose-normalized natural log transformed AUC_{inf} (data permitting) and AUC_{last} will be analyzed using a mixed effect model with treatment as fixed effects and subject as a random effect using a one-way analysis of variance (ANOVA). Estimates of the adjusted mean differences (Test-Reference) and corresponding 90% confidence intervals will be obtained from the model. The adjusted mean differences and 90% confidence intervals for the differences will be exponentiated to provide estimates of the ratio of adjusted geometric means (Test/Reference) and 90% confidence intervals for the ratios. SC doses are the Test treatments, and IV is the Reference treatment.

Subjects having positive ADAs will be analyzed separately to assess the effects of ADAs on RN909 (PF-06293620) concentrations. If there is no effect on the concentration versus time profiles, then these subjects will be included in the descriptive statistics of concentrations and PK parameters.

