SAD Cohorts: To assess the relationship between the PK parameters and dose, dose normalized AUC_{inf}, AUC_{last} and C_{max} will be plotted against dose (using a logarithmic scale), and will include individual subject values and the geometric means for each dose. Geometric means will have a different symbol than the individual values. The values will be dose normalized (to a 1 mg/kg dose) by dividing the individual values and raw geometric means by dose. A footnote will be added to the plots to indicate that geometric means are presented on the plot.

Absolute/Relative bioavailability will be estimated as the ratio of dose-normalized adjusted geometric means for SC and IV for AUC_{last} and AUC_{inf}.

MAD Cohorts: To assess the relationship between the PK parameters and dose, dose normalized AUC_τ and C_{max} on Days 1 and 57, and dose normalized C_{min} on Day 57, will be plotted against dose (using a logarithmic scale), and will include individual subject values and the geometric means for each dose. Geometric means will have a different symbol than the individual values. The values will be dose normalized (to a 1 mg/kg dose) by dividing the individual values and raw geometric means by dose. A footnote will be added to the plots to indicate that geometric means are presented on the plot.

Dose-normalized natural log transformed AUC (SAD): AUC_{inf} (data permitting) and AUC_{last} ; and $AUC\tau$ (MAD) will be analyzed using a mixed effect model with treatment as fixed effects and subject as a random effect using a one-way analysis of variance (ANOVA). Estimates of the adjusted mean differences (Test-Reference) and corresponding 90% confidence intervals will be obtained from the model. The adjusted mean differences and 90% confidence intervals for the differences will be exponentiated to provide estimates of the ratio of adjusted geometric means (Test/Reference) and 90% confidence intervals for the ratios. SC is the Test treatment, and the IV is the Reference treatment.

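### Absolute bioavailability is defined by dose-normalising every SC dose against one 1 mg/kg IV cohort, which needs dose-proportional kinetics that the protocol's own preliminary data do not support

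*Protocol*

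**What the plan says.** Protocol 9.3.2 gives the definition: "Absolute bioavailability (F) will be estimated as the ratio of dose-normalized adjusted geometric means for SC and IV", for AUClast and AUCinf. Log-transformed dose-normalised AUC goes into a one-way ANOVA with treatment as fixed effect. Differences are exponentiated to ratios with 90% confidence intervals, and "SC doses are the Test treatments, and IV is the Reference treatment".

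SAP 10.2.3.3 keeps the method but broadens the label: "Absolute/Relative bioavailability will be estimated as the ratio of dose-normalized adjusted geometric means for SC and IV for" AUClast and AUCinf. It refers to SC in the singular as the Test treatment, so it does not say whether there is one ratio per SC dose or one for all SC doses together.

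There is a single IV dose level. Protocol 3.1 says "the 1 mg/kg IV cohort will be evaluated but the 10 mg/kg IV cohort will not be conducted", and Table 5 lists SC cohorts at 0.3, 1, 3 and 6 mg/kg.

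On the kinetics seen so far, protocol 1.3.2 reports that Cmax and AUCinf "increased slightly greater than dose proportionally with increasing doses up to 6 mg/kg", and that mean terminal half-life was "ranging from 9 to 18 days as the doses increased from 0.3 to 3 mg/kg".

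Both documents plan plots of dose-normalised parameters against dose. Neither limits F to the matched 1 mg/kg dose, makes it conditional on proportionality, or says how to read it if kinetics are nonlinear.

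**The concern.** For one dose and route, AUC = F × dose / CL (with F = 1 for IV). The planned ratio at SC dose d is therefore F(d) × CL(1 mg/kg IV) / CL(d, SC). It reduces to F(d) only if clearance is the same in both arms. Dose normalisation does not create that equality; it assumes it. The protocol reports that exposure rose more than in proportion to dose.

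At 0.3, 3 and 6 mg/kg, the number labelled F would mix absorption with any change of clearance with dose. A value pooled over SC doses would depend on which cohorts were in the pool. The 90% interval covers sampling error and not this shift. F is among the PK parameters in the protocol Summary, and AUCinf and AUClast are the only parameters that SAP Table 4 marks for model-based analysis, so these ratios will be prominent PK outputs.

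**Working it through.** The documents state no value of F and no precision target for it, so there is no stated figure to reproduce.

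**Inputs.** Protocol Table 2 gives geometric mean AUCinf (µg·hr/mL) of 260 at 0.3 mg/kg, 1748 (CV 46%) at 1 mg/kg and 6606 (CV 45%) at 3 mg/kg, not calculated at 6 mg/kg. Its N, n row reads 6,2; 6,5; 6,6; 6,0. I take n as the number of subjects with an estimable AUCinf. All values are preliminary (cut-off 19 May 2015).

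**Step 1: dose-normalised AUCinf.**
- 0.3 mg/kg: 260 / 0.3 = 867
- 1 mg/kg: 1748 / 1 = 1748
- 3 mg/kg: 6606 / 3 = 2202

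The log-log slope from 0.3 to 3 mg/kg is ln(6606/260) / ln(10) = 1.40, where 1.0 is proportional. The pre-study predictions in Table 3 were proportional: 1144/0.3, 3812/1, 11435/3 and 22870/6 all give about 3812.

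**Step 2: ratio of apparent F between doses.** Both doses share one IV reference, so it cancels: Fapp(a) / Fapp(b) = AUCdn(a) / AUCdn(b).
- 3 vs 1 mg/kg: 2202 / 1748 = 1.26
- 1 vs 0.3 mg/kg: 1748 / 867 = 2.02
- 3 vs 0.3 mg/kg: 2202 / 867 = 2.54

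These follow whatever the IV cohort shows.

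**Step 3: approximate precision.** Log-normal model with CV 45.5% (midpoint of 46 and 45), so σ = √ln(1 + 0.455²) = 0.434; SE = σ√(1/n₁ + 1/n₂) with n = 2, 5, 6; t on 10 df = 1.812. The text gives no CV at 0.3 mg/kg. I assume the same value and show 30% and 60% as a range.

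| Contrast | Ratio | 90% CI, CV 45.5% | CV 30% | CV 60% |
|---|---|---|---|---|
| 3 vs 1 mg/kg | 1.26 | 0.78–2.03 | 0.91–1.74 | 0.69–2.32 |
| 1 vs 0.3 mg/kg | 2.02 | 1.04–3.89 | 1.29–3.15 | 0.87–4.68 |
| 3 vs 0.3 mg/kg | 2.54 | 1.34–4.83 | 1.65–3.92 | 1.12–5.77 |

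**Step 4: the sponsor's own predictions.** Protocol Table 4 gives predicted AUCtau of 1471, 4486 and 9448 at 75, 150 and 250 mg every 4 weeks. Per mg these are 19.6, 29.9 and 37.8, a rise of 37.8 / 19.6 = 1.93-fold. Section 1.3.3 predicts accumulation of 1.14 at 75 mg and, as I read it, about 1.4 and 1.6 at the higher doses. Under linear kinetics neither quantity would change with dose at a fixed interval. The predictions derive from the first four SAD cohorts, so they are not separate data, but they show that the sponsor's dose selection already treats the kinetics as nonlinear.

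**The case against.** The best reply is that the right estimate is already in the plan. The protocol names the SC doses in the plural as Test and fits treatment as a fixed effect, so the natural output is one ratio per SC dose, including 1 mg/kg SC against 1 mg/kg IV. The dose-normalised plots would show any trend beside the ratios. F is absent from the secondary endpoints in protocol 2.2.2, the study is exploratory, and no dose decision is tied to F. All of this stands. It makes the point one of definition and labelling, not of a missing analysis. But the plan also gives the name F to the ratios at 0.3, 3 and 6 mg/kg, and the SAP's singular wording permits a pooled value.

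The evidence is also thin, and this stands too. The 2.5-fold figure depends on apparently 2 subjects at 0.3 mg/kg, where 4 of 6 (67%) had no AUCinf. SAP 10.2.3.3 would suppress summary statistics there (more than 50% not calculated), although the ANOVA would still use the two values. Between 1 and 3 mg/kg the ratio is 1.26 and its interval includes 1. The protocol itself calls the departure slight.

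Some stronger readings are tempting, but the documents do not support them:
- **Nonlinear elimination as the established cause.** The half-life trend points that way, but no mechanism is given in the text available, and one IV dose cannot separate it from dose-dependent SC absorption.
- **F above 100% at 3 mg/kg.** This needs F at 1 mg/kg above 1/1.26 = 0.79, that is, an IV AUCinf below 2202. Table 3 predicts 7059. With that value the ratios would be 867/7059 = 0.12, 1748/7059 = 0.25 and 2202/7059 = 0.31, and Table 3's own predicted F is 3812/7059 = 0.54.
- **Extra distortion of AUClast because low doses fall below quantification sooner.** The available text gives neither AUClast values nor a quantification limit.
- **F as the purpose of the IV cohort.** Protocol 1.3.1 gives safety characterisation as the reason for dosing by both routes.

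**Conclusion.** The concern holds as a matter of definition. The planned ratio estimates F at 0.3, 3 and 6 mg/kg only under dose proportionality, which the preliminary data and the sponsor's MAD predictions speak against. On the Table 2 means, apparent F would differ about 1.26-fold between 1 and 3 mg/kg, which is compatible with no difference, and about 2.5-fold between 0.3 and 3 mg/kg, on very few subjects. Nothing can be computed for 6 mg/kg or for AUClast.

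This assumes that n in Table 2 counts subjects with an estimable AUCinf; the intervals also assume a similar CV at 0.3 mg/kg. The cause is open, but in neither case is there one F that the set of ratios estimates: if elimination depends on dose, the unmatched ratios are not F; if SC absorption does, F itself differs by dose.

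The matched 1 mg/kg contrast needs no proportionality across doses. Equal doses by two routes still give different concentrations, so matching reduces the influence of nonlinear clearance without fully removing it. The effect is confined to the secondary PK analysis; no primary safety conclusion depends on it.

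**What to change.** In SAP 10.2.3.3, and in protocol 9.3.2 if it is amended:

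1. Name 1 mg/kg SC (Test) against 1 mg/kg IV (Reference) as the estimate of absolute F, for AUCinf with AUClast as support.
2. Report the ratios at 0.3, 3 and 6 mg/kg as relative dose-normalised exposure and read them with the dose-proportionality plots.
3. State that SC doses are not pooled for F, and replace the combined absolute/relative label.
4. If F at other doses is wanted, take it from a PK model that allows nonlinearity, fitted to the SC and IV data together.

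Protocol section 9 lets the SAP modify the planned analyses, so a SAP change before database lock is enough.

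The cost is small. The matched contrast can be taken from the same ANOVA with all five active SAD groups kept. With 6 subjects per group and σ = 0.434, SE = 0.434 × √(1/6 + 1/6) = 0.250. On 25 residual df (t = 1.708) the 90% limits are the estimate divided and multiplied by exp(1.708 × 0.250) = 1.53, the same as for any planned per-dose ratio. Fitting only the two 1 mg/kg groups (10 df, t = 1.812) would give 1.57. Pooling all 24 SC subjects would give SE = 0.434 × √(1/24 + 1/6) = 0.198 and, on 28 df (t = 1.701), 1.40 if σ were unchanged. That gain in precision would be for a mixture of doses and not for F. Subjects without an estimable AUCinf would widen all of these.

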9.4. Pharmacodynamic Analysis

PD biomarker data will include fasting plasma glucose, fasting glucagon, fasting GLP-1, 24-hr glucose profile (finger-stick), HbA1c, fructosamine, 1,5-anhydroglucitol, post prandial glucose, insulin, C-peptide, glucagon and GLP-1 AUC after mixed meal tolerance test (MMTT, 4 hr) as well as mean daily glucose (MDG).

The relationship between changes in the values of these biomarkers with the pharmacokinetics of RN909 (PF-06293620) will be explored.

In order to minimize the impact of a single aberrant measurement to the baseline, where feasible, the baseline is defined as the average of at least two measurements prior to the first study drug administration as outlined in the statistical analysis plan.

9.5. Safety Analysis

All safety data analysis will be performed on the safety analysis set, which includes all enrolled subjects who receive at least one dose of study medication.

Adverse events, ECGs, blood pressure, pulse rate, continuous cardiac monitoring (SAD only), ambulatory blood pressure monitoring (MAD cohorts only), and safety laboratory data will be reviewed and summarized on an ongoing basis during the study to evaluate the safety of subjects. Any clinical laboratory, ECG, BP, and PR abnormalities of potential clinical concern will be described. Safety data will be presented in tabular and/or graphical format and summarized descriptively, where appropriate.

Medical history and physical exam information collected during the course of the study will be captured for inclusion into the study database, unless otherwise noted. Any untoward findings identified on physical exam conducted after the administration of the first dose of study medication will be captured as an adverse event, if those findings meet the definition of an adverse event. Data collected at Screening that is used solely for inclusion/exclusion criteria, such as laboratory data, ECGs and vital signs will be considered source data, and

will not be captured for inclusion into the study database, unless otherwise noted (note: screening physical exam is a comprehensive exam and will be captured in the study database as the baseline exam). Demographic data collected at Screening will be included in the study database.

Summary statistics and data listings will be provided for the following endpoints:

- Incidence of dose limiting or intolerable treatment related adverse events (AEs).
- Incidence, severity and causal relationship of treatment emergent AEs (TEAEs).
- Incidence of abnormal laboratory findings (clinical chemistry, hematology and urinalysis).
- Changes from baseline in safety laboratory assessments.
- Abnormal and clinically relevant changes in vital signs, BP, and ECG parameters.
- Incidence of anti-drug-antibodies (ADA).

9.5.1. Electrocardiogram (ECG) Analysis

ECG results will be reviewed by investigators in both the SAD and MAD portion of the study. In addition, all ECGs in the MAD portion will undergo central review. The analysis of ECG results will be based on subjects with baseline (Day 1 pre-dose) and on-treatment ECG data. ECG data will be summarized for heart rate (HR) and RR, PR, QRS and QT intervals by dose.

Post dose ECGs will be compared to the Day 1 pre-dose ECG for each subject, and any clinically significant changes will be recorded as adverse events and evaluated further, as clinically warranted.

Descriptive statistics (n, mean, median, standard deviation, minimum, and maximum) will be used to summarize the absolute QTcF value and changes from baseline in QTcF after treatment by treatment group (each RN909 dose and placebo), and by time point. For each subject and dose, the maximum change from baseline will be calculated as well as the maximum post-baseline value across time-points. Outlier analysis of the QTcF data will be conducted and summarized as follows:

- The number of subjects with maximum change from baseline in QTcF (<30, 30-60, and \geq 60 ms).
- The number of subjects with maximum post-dose (post-baseline) QTcF (<450, 450-<480, 480-<500, and \geq 500 ms).
- Changes from baseline for the ECG parameters QT interval, heart rate, QTc interval, PR interval and QRS interval will be summarized by treatment and time.

- The number (%) of subjects with maximum post dose QTc values and maximum increases from baseline in the following categories will be tabulated by treatment:

Safety QTc

	Borderline (msec)	Prolonged (msec)
Absolute Value	≥450 - <480	≥480
Absolute Change	30-<60	≥60

Shift tables will be provided for baseline vs. worst on study QTcF) using the maximum CTCAE Grade as well as tables of ECG abnormality at baseline (yes, no, not done: (n, %)). Subjects experiencing clinically-relevant morphological ECG changes will be summarized (including frequency and percentage).

The effect of drug concentrations on QTcF change from baseline may be explored graphically. Additional concentration-QTcF analyses may be performed.

In addition, the number of subjects with corrected and uncorrected QT values ≥500 msec will be summarized.

If more than one ECG is collected at a nominal time post dose (for example, triplicate ECGs), the mean of the replicate measurements will be used to represent a single observation at that time point. If any of the three individual ECG tracings has a QTc value ≥500 msec, but the mean of the triplicates is not ≥500 msec, the data from the subject's individual tracing will be described in a safety section of the study report in order to place the ≥500 msec value in appropriate clinical context. However, values from individual tracings within triplicate measurements that are ≥500 msec will not be included in the categorical analysis unless the average from the triplicate measurements is also ≥500 msec.

In addition, an attempt will be made to explore and characterize the relationship between plasma concentration and QT interval length using a PK/PD modeling approach. If a PK/PD relationship is found, the impact of subject factors (covariates) on the relationship will be examined.

